6.2 Withholding/Resuming Therapy

Study therapy will be withheld for the following adverse reactions:

a. A drug-related clinically significant toxicity \geq Grade 2, with the exception of the adverse reactions listed under requirement of permanent discontinuation of study therapy.

b. Grade 2 fatigue does not require the withholding of pembrolizumab.

c. When toxicity resolves or improves to \leq grade 1, therapy with pembrolizumab will resume.

d. In case toxicity does not resolve or improve to \leq grade 1 within 12 weeks after last administration of pembrolizumab, study drug discontinuation should be considered after discussion with SARC and overall study PI. If SARC, study PI and Merck are in agreement, patients who still have grade 2 toxicity at 12 weeks may continue on study only if asymptomatic and controlled.

e. Two dosing delays due to toxicity will be permitted. In the event of a third occurrence of a toxicity, which would require dosing delay, study therapy will be discontinued permanently.

f. For signs or symptoms of SJS or TEN, withhold KEYTRUDA® and refer the patient for specialized care for assessment and treatment.

Dose modification and toxicity management for immune-related AEs associated with pembrolizumab

AEs associated with pembrolizumab exposure may represent an immunologic etiology. These immune-related AEs (irAEs) may occur shortly after the first dose or several months after the last dose of pembrolizumab treatment and may affect more than on body system simultaneously. Therefore, early recognition and initiation of treatment is critical to reduce complications. Based on existing clinical trial data, most irAEs were reversible and could be managed with interruptions of pembrolizumab, administration of corticosteroids and/or other supportive care.

For suspected irAEs, ensure adequate evaluation to confirm etiology or exclude other causes. Additional procedures or tests such as bronchoscopy, endoscopy, skin biopsy may be included as part of the evaluation. Based on the severity of irAEs, withhold or permanently discontinue pembrolizumab and administer corticosteroids. Dose modification and toxicity management guidelines for irAEs associated with pembrolizumab are provided in Table 4.

Table 4: Dose Modification and Toxicity Management Guidelines for Immune-related AEs Associated with Pembrolizumab

General instructions:

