- 1. Corticosteroid taper should be initiated upon AE improving to Grade 1 or less and continue to taper over at least 4 weeks.
- 2. For situations where pembrolizumab has been withheld, pembrolizumab can be resumed after AE has been reduced to Grade 1 or 0 and corticosteroid has been tapered. Pembrolizumab should be permanently discontinued if AE does not resolve within 12 weeks of last dose or corticosteroids cannot be reduced to ≤ 10 mg prednisone or equivalent per day within 12 weeks.
- **3.** For severe and life-threatening irAEs, IV corticosteroid should be initiated first followed by oral steroid. Other immunosuppressive treatment should be initiated if irAEs cannot be controlled by corticosteroids.

| Immune-related AEs | Toxicity grade or conditions (CTCAEv4.0) | Action taken to pembrolizumab | irAE management with corticosteroid and/or other therapies | Monitor and follow- up |
|-----------------------|--|----------------------------------|---|---|
| Pneumonitis | Grade 2 Grade 3 or 4, or recurrent Grade 2 | Withhold Permanently discontinue | • Administer corticosteroids (initial dose of 1-2 mg/kg prednisone or equivalent) followed by taper | Monitor participants for signs and symptoms of pneumonitis Evaluate participants with suspected pneumonitis with radiographic imaging and initiate corticosteroid treatment Add prophylactic antibiotics for opportunistic infections |
| Diarrhea / Colitis | Grade 2 or 3 | Withhold | • Administer corticosteroids (initial dose of 1-2 mg/kg prednisone or equivalent) followed by taper | • Monitor participants for signs and symptoms of enterocolitis (ie, diarrhea, |

| Immune-related AEs | Toxicity grade or conditions (CTCAEv4.0) | Action taken to pembrolizumab | irAE management with corticosteroid and/or other therapies | Monitor and follow- up |
|---|---|----------------------------------|---|--|
| | Grade 4 | Permanently discontinue | | abdominal pain, blood or mucus in stool with or without fever) and of bowel perforation (ie, peritoneal signs and ileus). Participants with ≥ Grade 2 diarrhea suspecting colitis should consider GI consultation and performing endoscopy to rule out colitis. Participants with diarrhea/colitis should be advised to drink liberal quantities of clear fluids. If sufficient oral fluid intake is not feasible, fluid and electrolytes should be substituted via IV infusion. |

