| AEs | Grade 3 Grade 4 or recurrent Grade 3 | Withhold or discontinue based on the type of event. Events that require discontinuation include and not limited to: Gullain-Barre Syndrome, encephalitis Permanently discontinue | | confirm etiology and/or exclude other causes |

NOTE:

For participants with Grade 3 or 4 immune-related endocrinopathy where withhold of pembrolizumab is required, pembrolizumab may be resumed when AE resolves to \leq Grade 2 and is controlled with hormonal replacement therapy or achieved metabolic control (in case of T1DM).

Guidelines for Infusion Reactions

Dose modification and toxicity management of infusion-reactions related to pembrolizumab

Pembrolizumab may cause severe or life threatening infusion-reactions including severe hypersensitivity or anaphylaxis. Signs and symptoms usually develop during or shortly after drug infusion and generally resolve completely within 24 hours of completion of infusion. Dose modification and toxicity management guidelines on pembrolizumab associated infusion reaction are provided in Table 5.

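### Section 6.2d and Table 4 instruction 2 give opposite directions for a withheld immune-related event that is still grade 2, asymptomatic and controlled at 12 weeks

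*Combined protocol and SAP*

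**What the plan says.** Both rules stand in section 6.2, Withholding/Resuming Therapy.

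**Items a to f.** Item a sets the trigger for withholding: "A drug-related clinically significant toxicity" of grade 2 or higher, apart from reactions that already require permanent discontinuation. Item b exempts grade 2 fatigue. Item c restarts treatment at grade 1 or lower. Item d deals with toxicity that has not come down to grade 1 or lower within 12 weeks of the last administration. In that case "study drug discontinuation should be considered after discussion with SARC and overall study PI". Item d then adds that, with the agreement of SARC, the study PI and Merck, "patients who still have grade 2 toxicity at 12 weeks may continue on study only if asymptomatic and controlled".

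**Table 4.** Later in the section, under an unnumbered heading on immune-related events, the protocol states: "Dose modification and toxicity management guidelines for irAEs associated with pembrolizumab are provided in Table 4". General instruction 2 applies where drug has been withheld. It says that "pembrolizumab can be resumed after AE has been reduced to Grade 1 or 0 and corticosteroid has been tapered", and then: "Pembrolizumab should be permanently discontinued if AE does not resolve within 12 weeks of last dose". The same sentence also stops treatment if steroid cannot be brought to 10 mg prednisone equivalent a day or less within 12 weeks.

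**Note to Table 4.** One exception is given, "For participants with Grade 3 or 4 immune-related endocrinopathy where withhold of pembrolizumab is required". Those patients may restart at grade 2 or lower once the event is controlled by hormone replacement or, for type 1 diabetes, metabolic control is reached.

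**The concern.** The two rules use the same clock and cover overlapping events, but they differ in what they require at the end of it. One leaves stopping open and provides a route to continue at grade 2. The other directs permanent discontinuation and provides no such route. If no text ranks them, two sites facing the same patient can act in opposite ways and each cite the protocol, and neither decision can be classed as a deviation with confidence. This is a rule on permanent stopping for toxicity, so the main stakes are patient safety and uniform conduct. Section 12.1.3 foresees about 10 sites.

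**Working it through.** No arithmetic applies: the point depends on no sample size, error rate or event count. The check compares the two rules element by element and then applies them to one patient.

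| Element | 6.2d | Table 4, instruction 2 |
|---|---|---|
| Events covered | Clinically significant drug-related toxicity of grade 2 or higher (6.2a), less the permanent-discontinuation list | Immune-related events for which drug was withheld |
| Clock | 12 weeks from last administration | 12 weeks from last dose |
| Level that allows restart | Grade 1 or lower (6.2c) | Grade 1 or 0, steroid tapered |
| Action if that level is not reached | Discontinuation to be considered after discussion | Permanent discontinuation |
| Exception at grade 2 | Yes: asymptomatic, controlled, and three parties agree | None in the instruction |

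**Do the scopes overlap?** Yes. Item a is framed by drug-relatedness and severity, and it does not set immune-related events apart. The list in 6.1 removes only severe immune-mediated reactions in organs such as kidney and lung, so a grade 2 reaction of that kind stays within 6.2. Item f, on Stevens-Johnson syndrome and toxic epidermal necrolysis, shows that the lettered items are not confined to toxicity that has nothing to do with the immune system.

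**Does Table 4 use a different end point?** Instruction 2 speaks of the event resolving, without naming a grade. Its preceding sentence accepts grade 1 or 0 for restart, so grade 1 is presumably acceptable there too. The clear divergence is at grade 2.

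**Test patient.** Take grade 2 nephritis, for which Table 4 directs withholding. Twelve weeks after the last dose it is still grade 2, asymptomatic and controlled, with steroid at 10 mg a day or less.

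- Under 6.2d, the patient may continue if SARC, the study PI and Merck agree.
- Under instruction 2, pembrolizumab should be permanently discontinued.

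**Where the rules do not conflict:**

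- Grade 2 hyperthyroidism and grade 2 to 4 hypothyroidism: Table 4 says to continue, so no drug is withheld and instruction 2 is not reached.
- Grade 3 or 4 endocrinopathy that has come down to grade 2 or lower and is controlled: the note allows restart.
- Steroid that cannot be reduced to 10 mg a day or less: 6.1b and instruction 2 both stop treatment.
- Grade 2 events that are symptomatic or uncontrolled, or for which the three parties do not agree: the exception in 6.2d is not available.
- Drug-related toxicity that is not immune-related: only 6.2d applies.

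**The case against.** The strongest reply is that the two rules can be read together. Section 6.2 opens a separately headed part for immune-related events and sends their dose modification to Table 4, so a reader may apply the specific rule over the general one. Alternatively, Table 4 may be taken as the default, with 6.2d as a narrow case-by-case override. That would match 6.1a, where even listed severe reactions are decided finally after discussion with SARC. Each reading is reasonable, but they lead to opposite results for the test patient, and the protocol states neither. The objection therefore shows that the text can be repaired easily, not that it is consistent now.

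A second reply has more force as a limit. No site can continue such a patient alone, because 6.2d requires the agreement of three parties as well as asymptomatic, controlled toxicity. A reader might infer that discussion by itself is enough to continue. The text does not say that: discussion belongs to the decision on discontinuing, and agreement is the condition for continuing. This lessens the safety risk but does not remove the conflict, since a site following Table 4 would have no reason to seek agreement.

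Third, 6.2d speaks of continuing on study, which could be read as remaining in the trial off drug. It follows directly on a sentence about stopping study drug, in a section about resuming therapy, so continued treatment is the natural sense.

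**Conclusion.** The inconsistency is real and narrow. It concerns an immune-related event for which drug was withheld, outside the endocrine note, that is still grade 2 at 12 weeks, asymptomatic and controlled, with steroid at 10 mg a day or less. For that patient 6.2d permits continuation by three-party agreement and Table 4 instruction 2 directs permanent discontinuation. The documents do not say how many patients this would be. The conclusion assumes that 6.2d covers immune-related events, which its wording supports, and that continuing on study means continuing treatment.

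Three stronger inferences are not supported:

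- That the rules differ for every immune-related event still at grade 2. The non-conflicting cases listed above show otherwise.
- That the endocrine note is a third, contradictory threshold. It is an exception with a stated scope, which is ordinary drafting.
- That progression-free survival or response data are materially affected. Section 2.17 does end scheduled scans at treatment discontinuation, but section 10.3 adds an off-treatment disease evaluation if none was done within 30 days of the final visit. No effect is quantified, and it is probably small.

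The point is an internal inconsistency that should be corrected for patient safety and consistent conduct. It does not touch the sample size or the success criterion.

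**What to change.** Reconcile 6.2d with Table 4 general instruction 2. State in the text which events each rule covers, which takes precedence where both apply, and whether the three-party agreement in 6.2d is available for immune-related events. Which rule should govern is a clinical decision for the medical lead, and none is proposed here. The cost is a wording change in section 6.2 and Table 4 and a memo to sites. No design feature or analysis changes.

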7. ADVERSE EVENTS: LIST AND REPORTING REQUIREMENTS

Adverse event (AE) monitoring and reporting is a routine part of every clinical trial. The following list of AEs (Section 7.1) and the characteristics of an observed AE (Section 7.2) will determine whether the event requires expedited reporting **in addition** to routine reporting.

7.1 Adverse Events and Laboratory Abnormalities

7.1.1 Adverse Events (AEs)

7.1.1.1 Definition of Adverse Events

Per the International Conference of Harmonization (ICH), an AE is any untoward medical occurrence in a patient or clinical investigation patient administered a pharmaceutical product and which does not necessarily have a causal relationship with the treatment. An AE can therefore be any unfavorable and unintended sign (including an abnormal laboratory finding), symptom, or disease temporally associated with the use of a medicinal (investigational) product, whether or not considered related to the medicinal (investigational) product. Pre-existing conditions which worsen during a study are to be reported as AEs.

7.1.1.2 CTCAE term (AE description)

The descriptions found in the revised NCI Common Terminology Criteria for Adverse Events (CTCAE) version 4.0 will be utilized for AE reporting. All appropriate treatment areas should have access to a copy of the CTCAE version 4.0. A copy of the CTCAE version 4.0 can be downloaded from the CTEP web site (http://ctep.cancer.gov). All adverse events regardless of CTCAE grade must also be evaluated for seriousness.

7.1.1.3 Intensity

Intensity of all adverse events will be graded according to the NCI Common Terminology Criteria for Adverse Events v 4.0 (CTCAE) on a five-point scale (grades 1 to 5) and reported in detail on the CRF. Adverse events not listed on the CTCAE should be graded as follows:

| CTC Grade | Equivalent To: | Definition |
|---------------------|--------------------------------|---|
| Grade 1 | Mild | Discomfort noticed but no disruption of normal daily activity |
| Grade 2 | Moderate | Discomfort sufficient to reduce or affect daily activity; no treatment or medical intervention is indicated although this could improve the overall well-being or symptoms of the patient |
| Grade 3 | Severe | Inability to work or perform normal daily activity; treatment or medical intervention is indicated in order to improve the overall well-being or symptoms; delaying the onset of treatment is not putting the survival of the patient at direct risk. |
| Grade 4 | Life threatening/ disabling | An immediate threat to life or leading to a permanent mental or physical conditions that prevents work or performing normal daily activities; treatment or medical intervention is required in order to maintain survival. |
| Grade 5 | Death | AE resulting in death |

7.1.1.4 Drug-Adverse Event relationship

The causality relationship of study drug to the adverse event will be assessed by the investigator as either: **Yes or No.**

If there is a reasonable suspected causal relationship to the study medication, i.e. there are facts (evidence) or arguments to suggest a causal relationship, drugevent relationship should be assessed as **Yes**.

The following criteria should be considered in order to assess the relationship as **Yes:**

- Reasonable temporal association with drug administration
- Known response pattern to suspected drug
- Disappears or decreases on cessation or reduction in dose
- Reappears on re-challenge

The following criteria should be considered in order to assess the relationship as **No**:

- It does not follow a reasonable temporal sequence from administration of the drug
- It may readily have been produced by the patient's clinical state, environmental or toxic factors, or other modes of therapy administered to the patient
- It does not follow a known pattern of response to the suspected drug

• It does not reappear or worsen when the drug is re-administered.

7.1.1.5 Progression of Underlying Malignancy

Progression of underlying malignancy is not reported as an adverse event if it is clearly consistent with the suspected progression of the underlying cancer as defined by RECIST criteria, or other criteria as determined by protocol.

Hospitalization due solely to the progression of underlying malignancy should NOT be reported as a serious adverse event. Clinical symptoms of progression may be reported as adverse events if the symptom cannot be determined as exclusively due to the progression of the underlying malignancy, or does not fit the expected pattern of progression for the disease under study.

Symptomatic deterioration may occur in some patients. In this situation, progression is evident in the patient's clinical symptoms, but is not supported by the tumor measurements or, the disease progression is so evident that the investigator may elect not to perform further disease assessments. In such cases, the determination of clinical progression is based on symptomatic deterioration. These determinations should be a rare exception as every effort should be made to document the objective progression of underlying malignancy.

If there is any uncertainty about an adverse event being due only to the disease under study, it should be reported as an AE or SAE.

7.1.1.6 Treatment and Follow-up AEs

After the discontinuation of therapy with pembrolizumab continue to follow up AEs as follows:

Related AEs: Follow until one of the following occurs:

- Resolved or improved to baseline
- Relationship is reassessed as unrelated
- Death
- Start of new anti-cancer regimen
- Investigator confirms that no further improvement can be expected
- Clinical or safety data will no longer be collected or final database closure

Unrelated severe or life threatening AEs: Follow until one of the following occurs:

- Resolved or improved to baseline
- Severity improved to grade 2
- Death
- Start of new anti-cancer regimen
- Investigator confirms that no further improvement can be expected

• Clinical or safety data will no longer be collected or final database closure

Unrelated Grade 1 or Grade 2 AEs: Follow as clinically indicated.

The final outcome of each adverse event must be recorded on the eCRF.

7.1.2 Laboratory Test Abnormalities

7.1.2.1 Abnormal Laboratory Tests

Laboratory test results will be recorded as adverse events only if they meet criteria for CTCAE v 4.0 grade 1 or greater. These data will be captured on the adverse events eCRF.

Any laboratory result abnormality fulfilling the criteria for a SAE should be reported as such, in addition to being recorded as an adverse event on the eCRF.

7.1.2.2 Follow-up of Abnormal Laboratory Test

In the event of medically significant unexplained abnormal laboratory test values, the test should be repeated and followed until it has returned to the normal range, baseline value and/or an adequate explanation of the abnormality is found. If a clear explanation is established it should be recorded on the eCRF.

7.1.3 Serious Adverse Events

A serious adverse event is any adverse event occurring at any dose or during any use of pembrolizumab that:

- Results in death;
- Is life threatening;
- Results in persistent or significant disability/incapacity;
- Results in or prolongs an existing inpatient hospitalization;
- Is a congenital anomaly/birth defect;
- Is a new cancer (that is not a condition of the study);
- Is associated with an overdose;
- Is another important medical event

Progression of the disease under study is not considered an adverse event unless it results in hospitalization or death.

Any serious adverse event, or follow up to a serious adverse event, including death due to any cause other than progression of the cancer that occurs to any patient from the time treatment is started (Day 1) through 30 days following cessation of treatment, or the initiation of new anti-cancer therapy, whichever is earlier, whether or not related to pembrolizumab, must be reported within 24

hours to the SARC. SARC will notify Merck within 1 working day as outlined in the section 7.2.2.

Non-serious Events of Clinical Interest will be handled in the same manner as SAEs.

Additionally, any serious adverse event assessed by a site Investigator as related to pembrolizumab, regardless of the time elapsed, even if the study has been closed, should be reported to SARC and Merck (as outlined in the section 7.2.2).

A copy of all reports submitted to FDA will be sent to Merck at: Merck Global Safety, Attn: Worldwide Product Safety; [contact]

7.1.4 Pembrolizumab Overdose

For purposes of this trial, an overdose will be defined as any dose exceeding the prescribed dose for pembrolizumab by 20% (> 240 mg). No specific information is available on the treatment of overdose of pembrolizumab. In the event of overdose, pembrolizumab should be discontinued and the subject should be observed closely for signs of toxicity. Appropriate supportive treatment should be provided if clinically indicated.

7.1.5 Events of Clinical Interest

Events of clinical interest (ECI) are selected adverse events for this trial including:

1. An overdose of pembrolizumab, as defined in Section 7.1.4, that is not associated with clinical symptoms or abnormal laboratory results.

2. An elevated AST or ALT lab value that is greater than or equal to 3x the upper limit of normal and an elevated total bilirubin lab value that is greater than or equal to 2 x the upper limit of normal and, at the same time, an alkaline phosphatase lab value that is less than 2 x the upper limit of normal, as determined by way of protocol-specified laboratory testing or unscheduled laboratory testing.*

*Note: These criteria are based upon available regulatory guidance documents. The purpose of the criteria is to specify a threshold of abnormal hepatic tests that may require an additional evaluation for an underlying etiology.

